24. STATISTICAL ANALYSIS

The primary evaluation metric is the number of days free from hospitalization to day 28. We will finalize a statistical analysis plan which will consider mAb assignment, heterogeneity of treatment effect by patient characteristics and virus variants, and interaction with other treatments. Due to uncertainty in sample size, we will use a Bayesian adaptive design to ensure ability to provide statistical inference despite variable sample size.

25. ETHICAL CONSIDERATIONS

26. DATA MONITORING

UPMC clinical leadership will regularly monitor monthly reports on enrollment, patient characteristics, and outcomes. Leadership will also receive regular interim analyses from the adaptive statistical model to inform UPMC clinical policy.

27. CONSENT

As per EUA requirements, physicians will discuss the risks and benefits of mAbs and patients will consent to receive a mAb as part of usual care, should they desire mAb treatment. As per UPMC policy, the ordering physician reviews with patients the EUA Fact Sheet for each mAb and explain that the patient could receive any of the mAbs governed by FDA EUAs.

28. ADVERSE EVENTS and SERIOUS ADVERSE EVENTS

The EUAs require providers and/or their designees report all medication errors and serious adverse events potentially related to the antibodies within seven calendar days from the onset of the event. Serious adverse events are defined as death, life-threatening event, inpatient hospitalization or prolongation of existing hospitalization, substantial disruption of ability to conduct normal life functions, a congenital anomaly/birth defect, or an intervention to prevent death, a life-threatening event, hospitalization, disability, or congenital anomaly.

The EUAs require adverse event reports be submitted to FDA MedWatch via one of multiple methods. Copies of all FDA MedWatch forms are also to be sent to the antibody manufacturer.

Thus, there already exist reporting requirements for UPMC associated with mAb prescription. We will track and record these reported data and adverse events by mAb assignment.

29. SAFETY and RISK MITIGATION

The EUAs stipulate warnings including hypersensitivity, clinical worsening, and side effects. As per EUA requirements, warnings will be communicated by providers to patients, adverse events will be reported as above, and post-infusion clinical monitoring will be done. Administration of mAbs for patients with COVID-19 is routine care at UPMC, and their administration is not a research procedure.

30. MANAGEMENT of INFUSION REACTIONS

As per the EUAs, all participants should be monitored closely, as there is a risk of infusion reaction and hypersensitivity (including anaphylaxis) with any biological agent. Symptoms and signs that may occur as part of an infusion reaction include, but are not limited to fever, chills, nausea, headache, bronchospasm, hypotension, angioedema, throat irritation, rash including urticaria, pruritus, myalgia, and dizziness.

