### Trial Design Introduction

This trial is a platform trial investigating the relative safety and efficacy of multiple monoclonal antibody (mAB) regimens for the treatment of COVID-19 illness. This document describes the statistical details for the trial investigating the relative efficacy of multiple mAB regimens for patients meeting the FDA emergency use authorization (EUA).

The trial randomly allocates which mAB regimen patients receive and will evaluate their comparative effectiveness. Adaptive randomization will be utilized where mAB arms that are performing better will be given higher randomization probabilities. Different mAB arms may be added during the course of the trial and different mAB strategies may be dropped for futility. For the primary analysis of patients within the FDA EUA, there will be no control arm and all arms will be directly compared to all other arms for relative efficacy.

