## Primary Analysis Population

The primary analysis population, used for all adaptive analyses is the “As-Infused” population. The intent-to-treat population includes all patients randomized to an mAB arm. The “as-infused” population includes those patients that show up and are infused for their mAB. Given that all arms are a mAB arm, there is no anticipated relationship between lack of infusion and the assigned arm. Hence all adaptive analyses and safety analyses will be based on the as-infused population (where patients are coded by the mAB arm they receive). Patients who receive a randomized mAB allocation and are not infused may be tracked as a real-world evidence arm of outcome for a non-mAB control (see secondary analyses).

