**Trial Read-Outs:** There may be periodic “unblinding” of the trial results. When an arm is removed for inferiority or futility, the results for the inferior and the superior or the combination and its components of the two arms in the trigger will be unblinded and publicly released. The trial will continue and will utilize all data for any new inferences in the trial. Additionally, there may be need for periodic disclosure of the current trial results, such as when FDA revokes authorization for a given mAB. These disclosures will be made and the trial will continue unchanged.

**Response-Adaptive Randomization:** Assuming  $R$  arms available in the trial, response adaptive randomization will be utilized. The response adaptive randomization is conducted based on the probability that each arm has the optimal treatment effect (largest  $\theta$ ). Let  $q_a$  be the posterior probability that arm  $a$  is the optimal arm among the  $R$  arms in the randomization arm space:

$$q_a = \Pr(\theta_a = \max\{\theta_1, \dots, \theta_R\})$$

The randomization probabilities are weighted toward being equal to maintain sufficient randomization to each arm and because the assignment is open-label, to prevent any obvious patterns of assignments. The allocation probability for each arm is

$$\text{Allocation probability} = \frac{q_a + 1/R}{1+1}.$$

If an arm joins the trial and has no data on the primary endpoint, then the value of  $q_a$  for that arm is assigned to be  $1/R$  and the remaining arms probability of optimal summing to  $1 - \frac{1}{R}$ . This convention will create fixed randomization to a new arm in the trial until there is at least 1 observation of the primary endpoint for modeling.

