16. CONDUCT

17. DATA COLLECTION

The EUAs require that healthcare facilities and providers report therapeutic information and utilization data through HHS Protect, Teletracking, or National Healthcare Safety Network as directed by the US Department of Health and Human Services.

We will collect data including baseline demographics and underlying conditions, results of SARS-CoV-2 PCR or antibody testing, and initial care including mAb infusion completion. We will collect post-randomization healthcare encounters, including hospitalization, emergency department visits, ICU care, and other measures of healthcare utilization. We will use an electronic health record data collection process to augment existing UPMC data collection processes, as necessary.

All data will be handled and secured as per University of Pittsburgh and UPMC data guidelines.

There will be no research activities involving direct interaction with subjects performed as part of this evaluation.

In addition to the primary and secondary outcome data referenced in this submission, data collected will include the below areas. All data will be abstracted directly from the electronic health record and handled anonymously.

- mAb was administered, including date, time, and infusion completion as well as the location of the infusion
- Demographics (including age, sex, race, body weight, vaccination status)
- Healthcare encounters, including hospital and ICU admission status if applicable
- Medication usage and doses
- Hospital and ICU admission status, if applicable
- Administration of medications related to COVID-19, if applicable
- Remnant blood availability
- Laboratory and microbiology data, including COVID-19 testing done for clinical purposes

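### The only designated adverse event data are provider-attributed reports under open-label assignment, so acute reactions treated without admission have no attribution-free comparison between mAbs

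*Combined protocol and SAP*

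**What the plan says.** The SAP's Trial Design Introduction begins: "This trial is a platform trial investigating the relative safety and efficacy of multiple monoclonal antibody (mAB) regimens". Its Primary Analysis Population section adds: "Hence all adaptive analyses and safety analyses will be based on the as-infused population", with patients coded by the mAb they receive. It names no safety endpoint, time window or comparison. Both read-out appendices list hospital-free days (HFD) as the only endpoint, and neither contains a safety table.

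Protocol section 28 is the only place that describes adverse event data. Under the EUAs, providers or their designees must "report all medication errors and serious adverse events potentially related to the antibodies within seven calendar days". The definition is broad: "Serious adverse events are defined as death, life-threatening event, inpatient hospitalization or prolongation of existing hospitalization", among other items. The trial's own use of these data is one sentence: "We will track and record these reported data and adverse events by mAb assignment".

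The SAP pulls its randomization probabilities toward equality partly "because the assignment is open-label". Protocol section 20 says that patients are told which mAb they receive and that the physician may accept the assigned mAb or request another.

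Protocol section 17 describes data abstracted from the EHR for the evaluation. It covers the date, time, location and completion of administration. It also says: "We will collect post-randomization healthcare encounters, including hospitalization, emergency department visits, ICU care, and other measures of healthcare utilization", and lists "Medication usage and doses". Protocol section 7 defines HFD with death scored as -1, and lists all-cause mortality at 28 and 90 days, ED visits at 28 days and organ-support-free days at day 28.

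**The concern.** An event enters the section 28 stream only if a provider who knows the product judges it potentially related and files a report. Both steps can depend on the product, for instance on whether it is newly authorized or familiar. A comparison of reported events would then mix safety with reporting behaviour.

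The gap is specific. A reaction treated on the spot, with no admission, leaves HFD at 28. If it happens during an ED infusion, it may not register as a new ED visit. A reaction that does lead to an encounter is counted in the 28-day metrics, but among all the COVID-19 events of those 28 days. The EHR fields that could show such reactions without a relatedness judgment are already abstracted, and no acute-safety comparison uses them.

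At stake is whether the trial can say anything dependable about relative acute safety: it could overlook an excess on one mAb, or suggest an excess that comes only from reporting.

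**Working it through.** The documents give no safety event rate, reporting fraction or power, and protocol section 23 leaves sample size to case volume. There is no figure to reproduce, and every rate below is an assumption.

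**Missed difference.** Assume true acute event rates r₁ = 0.5% and r₂ = 1.5%, a reporting fraction f equal in both arms, and a common background b of unrelated events. The observed probability in arm k is p_k = f·r_k + b. With n per arm,

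power = Σ Bin(x₁; n, p₁) · Bin(x₂; n, p₂) over all pairs (x₁, x₂) with two-sided Fisher p < 0.05.

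| Scenario | p₁ v p₂ | Expected events, n = 1000 | Power | Expected events, n = 1800 | Power |
|---|---|---|---|---|---|
| f = 1, b = 0 | 0.5% v 1.5% | 5 v 15 | 54% | 9 v 27 | 84% |
| f = 0.6, b = 0 | 0.3% v 0.9% | 3 v 9 | 31% | 5.4 v 16.2 | 58% |
| f = 0.3, b = 0 | 0.15% v 0.45% | 1.5 v 4.5 | 10% | 2.7 v 8.1 | 27% |
| f = 1, b = 1% | 1.5% v 2.5% | 15 v 25 | 30% | 27 v 45 | 53% |
| f = 1, b = 5% | 5.5% v 6.5% | 55 v 65 | 13% | 99 v 117 | 22% |

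Rows 1 to 3 show what under-reporting costs even when it is equal in both arms. Row 4 shows what complete EHR capture gives if 1% of patients have an unrelated early encounter: about the same power as 60% reporting. Row 5 shows why a long window is a poor place to look for an acute reaction.

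**False difference.** Let the true rates be equal and the reporting fractions be 30% and 60%. The apparent rate ratio is 0.60/0.30 = 2.0. By the same exact method with 1000 per arm and true rates of 0.5% to 1.5%, Fisher p < 0.05 occurs in 2% to 16% of trials. The risk is larger for commoner events. Take a true rate of 5%, reporting of 50% v 25% (2.5% v 1.25% observed) and 967 per arm, which is half of 1935, a column total in the supplementary baseline table, used only as a plausible size. For the pooled two-proportion test,

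z = [0.0125·√967 − 1.96·√(2 × 0.01875 × 0.98125)] / √(0.025 × 0.975 + 0.0125 × 0.9875) = (0.3887 − 0.3760)/0.1916 = 0.07,

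so about 53% of trials show a difference in that one direction. With equal reporting the figure stays at the nominal 2.5%: a false difference needs reporting that differs by arm.

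**Assigned or received.** Section 28 tracks events by mAb assignment. The SAP codes safety analyses by mAb received. Because a physician can request another mAb, the two groupings can differ.

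**The case against.** The strongest reply is that much of this is already covered. Death and inpatient hospitalization lead the SAE definition, and both enter HFD whatever their cause. Mortality, ED visits and organ-support-free days are listed metrics, and protocol section 26 provides for monthly review of outcomes. This stands. A reader might infer that relative safety rests wholly on provider reports; the documents do not support that. What remains is acute reactions that do not reach those outcomes or are diluted in them.

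Second, the scope of safety is modest. The SAP goes on to describe itself as covering relative efficacy, the protocol objective is clinical and biological effect, and no rate ratio from reports is scheduled. This stands in part: a false difference arises only if the reports are compared between mAbs. But the SAP promises safety analyses, and these reports, kept by mAb, are the only adverse event data designated.

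Third, the EHR is no ideal comparator. Protocol section 17 does not list infusion reactions as an abstracted item. The SAP concedes that out-of-system hospitalizations may surface later. Early encounters will include COVID-19 progression, and row 4 shows the cost. This stands too.

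Fourth, a comparison by mAb received is not fully protected by randomization, because allocation is response-adaptive and physicians may request a product. It would be wrong to say that background events only dilute and never bias, so adjustment is needed.

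**Conclusion.** The point holds in a limited form, as a worthwhile and inexpensive improvement. The plan states a relative safety aim but designates only attribution-filtered reports made under open-label assignment. It specifies no attribution-free comparison for acute reactions treated without admission or diluted over 28 days.

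Two stronger readings should be resisted. One is that a real difference is likely to be missed: without an event rate or reporting fraction this cannot be derived, and on the assumed 0.5% v 1.5% even perfect capture gives only 54% power at 1000 per arm. The other is that a false signal is to be expected: open-label assignment makes product-dependent reporting possible, but nothing in the documents shows that it occurs.

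On the assumed rates, reporting of 60% or 30% lowers power from 54% to 31% or 10% at 1000 per arm, and from 84% to 58% or 27% at 1800. An assumed 1% background brings full capture down to 30% and 53%. For early encounters, the case for the EHR therefore rests on removing the relatedness judgment and product-dependent reporting more than on power.

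**What to change.** In protocol section 28 and the SAP's safety text, add to each read-out a comparison by mAb received, regardless of provider report or causality, of:

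- (a) drugs used to treat hypersensitivity, from a list fixed in advance, given after the start of administration on the same day;
- (b) new ED visit, admission or death within 24 h and within 72 h, excluding the index ED or infusion encounter.

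Adjust for the time epoch and ED/infusion-center terms already in the primary model, and report risk differences with 95% credible intervals. Keep the EUA reports as a supplementary listing. Reconcile tracking by mAb assignment in section 28 with coding by mAb received in the SAP. State also whether a patient with an incomplete infusion counts as infused, since the October read-out lists that under reasons for not being infused.

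The cost is an additional query on data already abstracted, provided that drug administration times are available, plus a short table. Clinical care does not change. The limits should be stated: (a) still depends on a clinician's decision to treat, though not on attribution or filing a report, and (b) is diluted by early COVID-19 progression and by out-of-system events found late.

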31. EXHIBITS

EUA fact sheets for health care providers:

<https://www.fda.gov/media/149534/download> (sotrovimab).

<https://www.regeneron.com/downloads/treatment-covid19-eua-fact-sheet-for-hcp.pdf> (casirivimab and imdevimab).

CONSORT Extension for Pragmatic Trials Checklist

Section	Item	Standard CONSORT Description	Pragmatic Trials Extension	Page
Title and abstract	1	How participants were allocated to interventions (e.g., “random allocation,” “randomized,” or “randomly assigned”)		Title page 1 & Abstract page 4-5
Introduction				
Background	2	Scientific background and explanation of rationale	Describe the health or health service problem that the intervention is intended to address and other interventions that may commonly be aimed at this problem	6
Methods				
Participants	3	Eligibility criteria for participants; settings and locations where the data were collected	Eligibility criteria should be explicitly framed to show the degree to which they include typical participants and/or, where applicable, typical providers (e.g., nurses), institutions (e.g., hospitals), communities (or localities e.g., towns) and settings of care (e.g., different healthcare financing systems)	8
Interventions	4	Precise details of the interventions intended for each group and how and when they were actually administered	Describe extra resources added to (or resources removed from) usual settings in order to implement intervention. Indicate if efforts were made to standardize the intervention or if the intervention and its delivery were allowed to vary between participants, practitioners, or study sites	8-10
			Describe the comparator in similar detail to the intervention	
Objectives	5	Specific objectives and hypotheses		6
Outcomes	6	Clearly defined primary and secondary outcome measures and, when applicable, any methods used to enhance the quality of measurements (e.g., multiple observations, training of assessors)	Explain why the chosen outcomes and, when relevant, the length of follow-up is considered important to those who will use the results of the trial	9
Sample size	7	How sample size was determined; explanation of any interim analyses and stopping rules when applicable	If calculated using the smallest difference considered important by the target decision maker audience (the minimally important difference) then report where this difference was obtained	10-11
Randomization—sequence generation	8	Method used to generate the random allocation sequence, including details of any restriction (e.g., blocking, stratification)		7-9
Randomization—allocation concealment	9	Method used to implement the random allocation sequence (e.g., numbered containers or central telephone), clarifying whether the sequence was concealed until interventions were assigned		7-9
Randomization—implementation	10	Who generated the allocation sequence, who enrolled participants, and who assigned participants to their groups		7-9
Blinding (masking)	11	Whether participants, those administering the interventions, and those assessing the outcomes were blinded to group assignment	If blinding was not done, or was not possible, explain why	10-11

Section	Item	Standard CONSORT Description	Pragmatic Trials Extension	Page
Statistical methods	12	Statistical methods used to compare groups for primary outcomes; methods for additional analyses, such as subgroup analyses and adjusted analyses		10-12
Results				
Participant flow	13	Flow of participants through each stage (a diagram is strongly recommended)—specifically, for each group, report the numbers of participants randomly assigned, receiving intended treatment, completing the study protocol, and analyzed for the primary outcome; describe deviations from planned study protocol, together with reasons	The number of participants or units approached to take part in the trial, the number which were eligible, and reasons for non-participation should be reported	11-12
Recruitment	14	Dates defining the periods of recruitment and follow-up		11-12
Baseline data	15	Baseline demographic and clinical characteristics of each group		13-14
Numbers analyzed	16	Number of participants (denominator) in each group included in each analysis and whether analysis was by “intention-to-treat;” state the results in absolute numbers when feasible (e.g., 10/20, not 50%)		14
Outcomes and estimation	17	For each primary and secondary outcome, a summary of results for each group and the estimated effect size and its precision (e.g., 95% CI)		17-20
Ancillary analyses	18	Address multiplicity by reporting any other analyses performed, including subgroup analyses and adjusted analyses, indicating which are prespecified and which are exploratory		17-20
Adverse events	19	All-important adverse events or side effects in each intervention group		20
Discussion				
Interpretation	20	Interpretation of the results, considering study hypotheses, sources of potential bias or imprecision, and the dangers associated with multiplicity of analyses and outcomes		21-23
Generalizability	21	Generalizability (external validity) of the trial findings	Describe key aspects of the setting which determined the trial results. Discuss possible differences in other settings where clinical traditions, health service organization, staffing, or resources may vary from those of the trial	21-23
Overall evidence	22	General interpretation of the results in the context of current evidence		21-23

Statistical Analysis Plan Final Version 1.1, July 26, 2021
Design for UPMC Antibody Treatment and Evaluation Center
Berry Consultants

Summary of Statistical Analysis Plan Changes for Amendment 1 on July 26, 2021

Page #	Plan Section	Reason for Change
3	Model Convergence	Clarify handling of model convergence.
6	Modeling Treatment Heterogeneity	Additional use of Pennsylvania statewide variant data as a surrogate for patient-level variant data
6	Appendix Read-out	Provided details of the final analytical read-out.

Trial Design Introduction

This trial is a platform trial investigating the relative safety and efficacy of multiple monoclonal antibody (mAb) regimens for the treatment of COVID-19 illness. This document describes the statistical details for the trial investigating the relative efficacy of multiple mAb regimens for patients meeting the FDA emergency use authorization (EUA).

The trial randomly allocates which mAb regimen patients receive and will evaluate their comparative effectiveness. Adaptive randomization will be utilized where mAb arms that are performing better will be given higher randomization probabilities. Different mAb arms may be added during the course of the trial and different mAb strategies may be dropped for futility. For the primary analysis of patients within the FDA EUA, there will be no control arm and all arms will be directly compared to all other arms for relative efficacy.

Treatment Arms

The trial may investigate multiple mAb strategy arms. Let k the number of active mAb strategies at any time in the trial. We label these arms as $a=1, \dots, k$.

Primary Endpoint

The primary endpoint in the trial is hospital-free days (HFDs). The endpoint is a composite of death and number of days alive and free of the hospital. The worst outcome is that a patient dies within 28 days. This outcome is labeled as a -1 HFDs. For patients who do not die within 28 days the primary endpoint is the number of days alive and free of hospitalization. For patients alive at day 28 the endpoint is characterized as an integer value with the number of days free of hospital admission, with possible values $0, 1, 2, 3, \dots, 28$. For statistical analyses the endpoint is modeled as an ordered categorical variable. If a patient has intervening days free of hospital and then has a re-hospitalization the patient will be given credit for the intervening days as “free” of the hospital.

Primary Analysis Population

The primary analysis population, used for all adaptive analyses is the “As-Infused” population. The intent-to-treat population includes all patients randomized to an mAb arm. The “as-infused” population includes those patients that show up and are infused for their mAb. Given that all arms are a mAb arm, there is no anticipated relationship between lack of infusion and the assigned arm. Hence all adaptive analyses and safety analyses will be based on the as-infused population (where patients are coded by the mAb arm they receive). Patients who receive a randomized mAb allocation and are not infused may be tracked as a real-world evidence arm of outcome for a non-mAb control (see secondary analyses).

Primary Analysis Model

The primary analysis model for the primary endpoint is a cumulative proportional odds model. Let the probability of an outcome of less than or equal to y be $\pi_y = \Pr(Y \leq y)$. Let a be the indicator of treatment arm ($a=1,\dots,k$). The model adjusts for the following baseline variables:

1. ED or infusion center (0=infusion center, 1=ED)
2. Age (with categories of <30, 30-39, 40-49, 50-59, 60-69, 70-79, and ≥ 80 ; 60-69 will be used as the referent)
3. Sex (sex at birth, male is the referent)
4. COVID-19 variant (0=unknown/uncollected (referent), categorical endpoint for each known variant)
5. Time (two-week epochs of time are used for adjustments; the most current 4-week period is the referent)

The primary analysis model is based on a cumulative logistic regression, where $\pi_y = \Pr(Y \leq y)$, where

$$\log\left(\frac{\pi_y}{1-\pi_y}\right) = \alpha_y - \theta_a \delta_{[a]} - \sum_{v=1}^4 \beta_{vj} \delta_{vj} - \lambda_{[time]}; \quad y = -1, 0, 1, 2, \dots, 27.$$

The additive covariate effects across all treatment arms for each patient are modeled through the β parameters. The δ parameters are indicator functions for the treatment arm and covariate values for the baseline covariates. The efficacy of the treatment arms is modeled with the θ parameters. The ordinal effect parameters (α_y) are modeled with a Dirichlet distribution with equal weight on each outcome and a sum of 1.

The baseline covariate effects are modeled with independent weak prior distributions:

$$\beta_{vj} \sim N(0, 10^2), \quad v = 1, \dots, 4; \quad j = 1, \dots, n_v.$$

The appropriate coefficients will be set to 0 within each covariate for identifiability (the goal will be the largest category set to 0).

The effects of time are adjusted within the model using two-week epochs and a smoothing model over time. The modeling of the time effects is set up with the most current period (2 epochs combined being the most recent month are set to 0):

$$\begin{aligned} \lambda_1 &\equiv \lambda_2 \equiv 0 \\ \lambda_2 - \lambda_1 &\sim N(0, 0.15^2) \\ \lambda_T - 2\lambda_{T-1} + \lambda_{T-2} &\sim N(0, \tau_\lambda^2); \quad T \geq 3 \\ \tau_\lambda^2 &\sim IG(0.25, 0.00562) \end{aligned}$$

The prior distributions for the mAb treatment effects are weak:

$$\theta_a \sim N(0, 10), \quad a = 1, \dots, k.$$

Arms

One of the treatment arms is selected as the referent arm for treatment effects and assigned a treatment effect of $\theta_a = 0$. The treatment arm at the first adaptive analysis with the largest sample size will be specified as the referent arm for the remainder of the trial.

Model Convergence

Given the complexity of the model, conventions may be taken by the analysis team if there are convergence issues or model stability issues. For example, there may be outcome categories in the 30 possible primary outcome values (e.g., k number of hospital-free days, patient death) that do not occur. If this happens at analysis, the cells will be

combined to achieve model convergence. For example, if the 4 hospital-free day outcome value does not occur it will be combined with 3, and so on, until every cell has occurred. Additional model stability conventions will be taken to preserve the model stability.

Missing and Partial Data

If there are missing covariates for a patient in the as-infused patient population, the following conventions will be used.

1. If the treatment arm is missing the patient will be ignored.
2. If a baseline covariate is missing the referent value for that covariate will be used

For all model analyses, only patients who have achieved 28-days of follow-up from the date of the index infusion will be used in the analysis. No use or imputation of patient data for patients with less than 28 days will be conducted.

Given the EHR-based data summaries there will be no missing outcome data. If there is deemed to be a corrupted outcome that patient will be ignored. Some patients may have 28 hospitalization-free days that at subsequent analyses are found to have out of system hospitalizations. The data will be updated at future analyses.

Trial Inferences

For the primary analysis, there is no “control” treatment and so all inferences are made comparing the individual treatment arms to each other. The main quantity of interest will be the relative odds ratio between any two treatments arms

$$OR_{ij} = \exp(\theta_i)/\exp(\theta_j).$$

The posterior probability that the odds ratio for arm i compared to arm j is greater than 1 (signifying that treatment i is superior to treatment j) is used as a comparison between arms. Additionally, the posterior mean and 95% confidence interval between arms will be used to summarize relative treatment effects.

Adaptive Design

The trial design is adaptive. A sequence of frequent interim analyses will be conducted as a function of enrollment rate. The expectation is to conduct monthly adaptive analyses. The following decision triggers will be addressed at each adaptive analysis:

Arm Inferiority: If one of the arms has a 99% chance of being inferior to any of the other available arms then the inferior arm will be declared inferior and may be removed from the trial. There may be conditions of the pandemic (e.g., variant frequency, new variants) or drug supply concerns that an arm is retained.

Equivalence: Any two arms in the trial may reach a declaration of equivalence. It is anticipated that no actions would take when equivalence is reached but a declaration and public disclosure may be made. There is a sliding scale of equivalence with different levels of equivalence bounds. A declaration of equivalence will be tied to the equivalence level. Equivalence with a bound of d is declared if the posterior probability of the odds ratio is with d is at least 95%:

$$\Pr\left(\frac{1}{1+\delta} \leq OR_{ij} \leq 1 + \delta\right) \geq 0.95$$

The following levels are pre-defined:

1. The first level of equivalence occurs when there is 95% posterior probability that the odds-ratio is within a bound of $d=0.25$

2. The second level of equivalence occurs when there is a 95% posterior probability that the odds-ratio is within a bound of $d=0.20$
3. The third level of equivalence occurs when there is a 95% posterior probability that the odds-ratio is within a bound of $d=0.15$
4. The fourth level of equivalence occurs when there is a 95% posterior probability that the odds-ratio is within a bound of $d=0.10$
5. The fifth level of equivalence occurs when there is a 95% posterior probability that the odds-ratio is within a bound of $d=0.05$

Combination Futility: When combinations of mAb are used the combination therapy may be compared to individual components of the combination. If there is more than a 95% probability that the effect of the combination mAb is no better than a 20% improvement in the odds ratio compared to each individual component then the combination may be declared *not clinically relevantly superior (futile)* to the individual components and the combination will be stopped. The comparison between a combination and the individual components will be declared when the combination is included within the platform trial.

Trial Read-Outs: There may be periodic “unblinding” of the trial results. When an arm is removed for inferiority or futility, the results for the inferior and the superior or the combination and its components of the two arms in the trigger will be unblinded and publicly released. The trial will continue and will utilize all data for any new inferences in the trial. Additionally, there may be need for periodic disclosure of the current trial results, such as when FDA revokes authorization for a given mAb. These disclosures will be made and the trial will continue unchanged.

Response-Adaptive Randomization: Assuming R arms available in the trial, response adaptive randomization will be utilized. The response adaptive randomization is conducted based on the probability that each arm has the optimal treatment effect (largest θ). Let q_a be the posterior probability that arm a is the optimal arm among the R arms in the randomization arm space:

$$q_a = \Pr(\theta_a = \max\{\theta_1, \dots, \theta_R\})$$

The randomization probabilities are weighted toward being equal to maintain sufficient randomization to each arm and because the assignment is open-label, to prevent any obvious patterns of assignments. The allocation probability for each arm is

$$\text{Allocation probability} = \frac{q_a + 1/R}{1+1}.$$

If an arm joins the trial and has no data on the primary endpoint, then the value of q_a for that arm is assigned to be $1/R$ and the remaining arms probability of optimal summing to $1 - \frac{1}{R}$. This convention will create fixed randomization to a new arm in the trial until there is at least 1 observation of the primary endpoint for modeling.

Modeling Treatment Heterogeneity

During the course of the trial, and during a trial read-out, inferences of relative treatment effect by different subgroups may be utilized. In these cases, the treatment effect is modeled as a function of subgroup within the single larger model. Each level of the subgroup will be identified and added as a covariate in the model and then the treatment effect, θ_{as} , will be modeled separately within each subgroup, $s = 1, \dots, S$, as $\theta_{a1}, \theta_{a2}, \dots, \theta_{aS}$, with hierarchical prior distribution:

$$\theta_{as} \sim N(\mu_a, \tau_a^2), a = 1, \dots, k; s = 1, \dots, S.$$

$$\mu_a \sim N(0, 10^2); \tau_a^2 \sim IG(0.25, 0.1).$$

Assessment of COVID-19 Variants

The COVID-19 variant type is a predefined subgroup for analysis. The variant type for each patient is unknown at baseline, but samples will be collected and reported upon sequencing. The posterior median odds ratios and 95% credible intervals will be reported for each arm comparison within each variant subset. In addition, because a large percentage of mAb infused patients will not have variant sequencing data (at least in near real time), a second “surrogate” approach will be used to compare the relative efficacy of the mAb regimens in the full treated population over time and by variant type.

Using Pennsylvania statewide data, we will estimate the prevalence of a given variant type by time. Then, we can categorize patients into various time epochs relative to the variant prevalence. These categories will be provided based upon the changing distributions over time in our region.

To consider the internal validity of this “surrogate” approach, we will use data from the subset of patients with actual genotype sequencing, compare the proportion of patients with prevalence of the variant type of interest across levels of the surrogate classification (i.e., Cochran Mantel-Haenszel test of trend).

Adaptive Analyses Reporting

The primary analysis will read out with summaries of the potential arm triggers for each arm actively in the “regimen space.” These summaries will include the probability each mAb is optimal in the active regimen space and the randomization probabilities.

A second analysis will be conducted with all arms (even those closed) in the regimen space, to report the probability each regimen is optimal among the larger regimen space.

As the EHR system contains the same covariate and baseline data for both mAb treated and untreated patients, we have continuously updated flags for each patient in the system as being “mAb eligible” (or not) based on EUA criteria on the date the patient became COVID-19 positive. With appropriate selection, this affords 2 untreated control groups for analysis that we will describe using mean (SD), median [IQR}, and proportions, as appropriate: mAb eligible patients who were never randomly assigned to a respective mAb regimen, and mAb eligible patients who were randomly assigned to a mAb regimen yet did not receive treatment.

Readout

Introduction

This document describes the detail of the analysis read-out from July 26, 2021. This document is an appendix to the Statistical Analysis Plan for the “UPMC Antibody Treatment and Evaluation Center” with the details for this analysis read-out.

- We will analyze and report three treatment arms (below) as the first two have been administratively closed to enrollment due to FDA decisions.
- Unblinded data from this and prior interim analyses can be shared with investigators after the last randomized allocations (June 25) to the two mAb treatment arms closed by FDA.
